## Sample Size Estimation

As this study is an observational investigation, the final sample size will depend on the number of patients ultimately enrolled.

Retrospective component: Data will be collected from patients who underwent thoracoscopic surgery at the Department of Thoracic Surgery, Tongji Hospital, Tongji Medical College, Huazhong University of Science and Technology, between January 2024 and December 2024, with a total of 2,000 cases included.

Prospective component: Based on previous similar studies, the anticipated sample size is approximately 50–100 patients. Sample size calculation will be performed using MedCalc software.

Statistical parameters for sample size calculation: Significance level (Type I error,  $\alpha$ ) = 0.01; Power (1 – Type II error,  $1-\beta$ ) = 0.90; Area under the ROC curve (AUC, AZ) = 0.85; Ratio of negative to positive groups = 0.176.

The calculation results are summarized as follows:

		Significance level (Type I error, $\alpha$ )			
		0.20	0.10	0.05	0.01
Power (1- $\beta$ )	0.20	14+3	20+4	27+5	42+8
	0.10	18+4	25+5	32+6	48+9
	0.05	21+4	29+6	37+7	54+10
	0.01	29+6	38+7	46+9	66+12

Based on calculations performed using MedCalc software, the required total sample size for this study is 57 patients. To account for potential attrition during the study, such as loss to follow-up or incomplete data, an additional 10% of participants will be included. Consequently, for each type of thoracic surgery, 63 patients will be enrolled, resulting in a total of  $63 \times 4 = 252$  patients for the study.

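### The protocol gives sizes for the prospective component that cannot all hold (50–100, 57 as a study total, 252), and does not say whether 57 is per surgery type or pooled

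*Protocol*

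**What the plan says.** All the figures stand in the protocol section Sample Size Estimation.

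- A general opening remark, made before either component is introduced: "the final sample size will depend on the number of patients ultimately enrolled".
- For the prospective component: "Based on previous similar studies, the anticipated sample size is approximately 50–100 patients".
- The inputs to the calculation: alpha 0.01, power 0.90, "Area under the ROC curve (AUC, AZ) = 0.85" and "Ratio of negative to positive groups = 0.176".
- The result, 48+9 in the bold cell of the table: "the required total sample size for this study is 57 patients".
- After a 10% allowance for attrition: "for each type of thoracic surgery, 63 patients will be enrolled", and 63 × 4 = 252 for the whole study.

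The table labels its rows as power (1−β), with values 0.20, 0.10, 0.05 and 0.01. The chosen cell sits in the row marked 0.10, while the text gives power as 0.90.

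The section does not explain the factor 4. It matches the four kinds of procedure listed under Inclusion Criteria (wedge resection, segmentectomy, lobectomy, mediastinal surgery).

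**The concern.** Two different numbers, 57 and 252, are each presented as the size of the study, and they differ by a factor of 252/57 = 4.4. The range anticipated for the prospective component ends at 100, which is 100/252 = 40% of the closing figure. The same number, 57, is a total in one sentence and the requirement for a single surgery type two sentences later.

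At stake is whether the study can show that it reached its planned size. A team that ended prospective recruitment at 57, at 100 or at 252 could cite this section in each case. Whether the smaller sizes would be adequate depends on whether the AUC is to be estimated within each surgery type or over all types together, and the protocol does not say.

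**Working it through.** **Inputs.** From Sample Size Estimation: alpha 0.01, power 0.90 (z = 1.2816), AUC 0.85, negative-to-positive ratio r = 0.176. The protocol states neither the null AUC nor the sidedness. I assume a null of 0.5 and a two-sided test (z = 2.5758), because these reproduce the table.

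**Formula.** Large-sample Hanley-McNeil variance per positive case:

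V(A) = (Q1 − A²)/r + (Q2 − A²), with Q1 = A/(2 − A) and Q2 = 2A²/(1 + A).

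- V(0.5) = 0.08333/0.176 + 0.08333 = 0.5568; square root 0.7462.
- V(0.85) = 0.01663/0.176 + 0.05858 = 0.1531; square root 0.3912.

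**Step 1: reproduce 57.**

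n(positive) = [(2.5758 × 0.7462 + 1.2816 × 0.3912)/0.35]² = [(1.9221 + 0.5014)/0.35]² = 47.9, so 48.

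n(negative) = 0.176 × 48 = 8.4, so 9. Total 57.

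The same formula reproduces all 16 cells of the table, provided the row values are read as β. One-sided versions do not match. Required numbers also rise as the row value falls, as they must for β and cannot for power. The row heading is therefore a label error; no number changes.

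**Step 2: the chain to 252.** 57 × 1.10 = 62.7, so 63; 63 × 4 = 252. The arithmetic is right. The fault is that its starting figure is called the study total.

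**Step 3: power at the competing sizes.** With total T in one analysis, n(positive) = T/1.176 and

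power = Φ{[0.35 × √n(positive) − 1.9221]/0.3912}.

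Example, 25 in one analysis: n(positive) = 21.26; (0.35 × 4.611 − 1.9221)/0.3912 = −0.788; power 21.5%.

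The second figure in each pair is from the finite-sample form of the same variance.

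| Prospective total | Per type (equal split) | Power per type | Power if pooled |
|---|---|---|---|
| 50 | 12.5 | 2.3% / 2.2% | 82% / 80% |
| 57 | 14.25 | 3.6% / 3.4% | 91% / 89% |
| 63 | 15.75 | 5.1% / 4.7% | 95% / 94% |
| 100 | 25 | 21.5% / 19.8% | over 99% |
| 228 | 57 | 90.6% / 89.4% | over 99% |
| 252 | 63 | 94.9% / 94.2% | over 99% |

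The 228 row is the 252 plan with 57 evaluable in each type. At 12.5 to 25 per type the ratio leaves only 1.9 to 3.7 negatives, so the normal approximation is rough there.

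**The case against.** The strongest defence is that 57, 63 and 252 form a single derivation and that the section ends on 252. On that view 50–100 is only a preliminary guess: it is worded as anticipated and approximate, and it comes before the calculation. Since 57 and 63 both lie inside 50–100, the range may even anticipate the per-type number. Read that way, power per type is about 80% at 50 and over 99% at 100.

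Much of this stands. The chain is one derivation with a mislabelled start, not several rival calculations. The opening remark about final enrolment is general and is not a further competing size. But the defence has to read 57 as per type against the text, which calls it the total for the study, and 50–100 as per type where the text gives it for the prospective component. Nothing in the section says either.

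Three stronger conclusions are tempting but not supported.

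- A reader might infer that 90% power is promised for each surgery type. The protocol gives 0.90 for the calculation only. Study Procedures relates PVB and MMP3 to complications without a split by type, and the statistical section uses the AUC only where appropriate. The per-type reading rests on the factor 4 alone.
- A reader might take 2% to 20–22% as secure. It needs an equal split, a null of 0.5, a two-sided test and the same ratio in every type. A one-sided test gives about 6–38%. A binormal simulation of the Mann-Whitney z test gave 0% to about 32–34%. A Wald test gave about 59–77%, but its type I error at these sizes was not checked.
- A reader might infer that recruitment could be stopped on how the data look. No interim look is described, and Study Procedures gives a window from March 2025 to May 2028.

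**Conclusion.** The point holds as an inconsistency in the stated size, and that part needs no power assumption: 50–100, a study total of 57 and a study total of 252 cannot all describe the prospective component. The calculation of 57 is correct under its own inputs.

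The consequence depends on the analysis intended. Per type, a total of 50–100 falls far short of the 0.90 used in the calculation, subject to the limits on the low-power figures noted above. Pooled, the same total is broadly adequate, and it is then the multiplication by 4 that lacks a basis. Either way the section must change.

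Severity: should be fixed. A loss of power is conditional on an analysis that the protocol does not specify, so nothing stronger is warranted.

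**What to change.** State whether the AUC analysis, and so the 57, is per surgery type or pooled, and give one governing prospective target. Only the sponsor can settle which is meant.

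- **If per type:** describe 57 as the number required per surgery type instead of the study total, keep 63 per type and 252 in all, and delete the 50–100 range.
- **If pooled:** keep 57 evaluable (63 enrolled) as the minimum for the stated power, and remove the factor 4 or justify it separately.
- **In either case:** if fewer will be enrolled than the chosen target, restate the power for that size. Limit the opening remark on final enrolment so that it does not override the prospective target. Relabel the table rows as β.

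The cost is protocol wording only. The downside is less freedom over the final size, or a lower stated power if the smaller range is the real plan.

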### **Prospective Analysis (Mar 2025 – May 2028)**

Screen patients meeting the inclusion criteria and immediately collect baseline data, including sex, age, occupation, past medical history, symptoms and onset time, vital signs, MMP3 levels, complete blood count, liver and kidney function, blood gas analysis, coagulation profile, and postoperative inflammatory markers.

Record postoperative outcomes at 24 and 48 hours, including cough and pain scores, time to first flatus and defecation, length of hospital stay, and the incidence of 30-day postoperative complications, including pulmonary infection, respiratory failure, pleural effusion, atelectasis, bronchospasm, pneumothorax, aspiration-induced lung injury, pulmonary embolism, bronchopleural fistula, and acute respiratory distress syndrome (ARDS).

Evaluate the association between PVB and MMP3 levels with postoperative thoracic complications and validate these findings against the results of the retrospective analysis.

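### The 90% power per surgery type assumes a fixed 48+9 split that the prospective cohort does not control; averaged over the random split it is about 81% with 57 evaluable patients and 87% with 63

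*Protocol*

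**What the plan says.** The Sample Size Estimation section of the protocol sizes the prospective part on a single ROC curve. The inputs are alpha 0.01, power 0.90, "Area under the ROC curve (AUC, AZ) = 0.85" and "Ratio of negative to positive groups = 0.176". The highlighted table cell is 48+9, and the text concludes: "Based on calculations performed using MedCalc software, the required total sample size for this study is 57 patients". For attrition, "an additional 10% of participants will be included", and then "for each type of thoracic surgery, 63 patients will be enrolled", giving 63 × 4 = 252. The power is therefore claimed separately for each surgery type.

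The Prospective Analysis section describes how patients enter: "Screen patients meeting the inclusion criteria and immediately collect baseline data". Complications are then recorded up to 30 days after surgery. The protocol sets no quota of positives and negatives, and no rule to recruit until the smaller class reaches a given size. It does not say which patients are positive.

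**The concern.** A calculation that returns 48+9 gives the power when exactly 48 patients fall in one class and exactly 9 in the other, as a case-control sample could arrange. In a cohort whose outcome emerges after enrolment, only the total is under control. Nearly all the information about the AUC comes from the smaller class, and power falls faster below 9 than it rises above 9. Averaging over the possible splits must therefore give less than the fixed-split figure.

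At stake is how a negative result in one surgery type is read. At about 81% power, a marker with a true AUC of 0.85 is missed about 19% of the time, against the 10% that the plan implies.

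**Working it through.** **Inputs from the protocol (Sample Size Estimation).** AUC 0.85; alpha 0.01; negative-to-positive ratio 0.176, so the negative fraction is 0.176/1.176 = 0.1497; 57 evaluable; 63 enrolled per type (57 × 1.1 = 62.7, rounded up; 63 × 0.9 = 56.7).

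**Assumptions.** The null AUC and the sidedness are not stated. I take 0.5 and two-sided, because these reproduce the table; one-sided testing gives 42+8 for the highlighted cell.

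**Formula (Hanley-McNeil).** With p positives and n negatives, Q₁ = A/(2−A) and Q₂ = 2A²/(1+A):

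V(A) = [A(1−A) + (p−1)(Q₁−A²) + (n−1)(Q₂−A²)] / (pn)

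Power = Φ{ [0.85 − 0.5 − 2.576·√V(0.5)] / √V(0.85) }

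**Step 1: reproduce the plan's figure.** For p = 48, n = 9: Q₁ = 0.7391, Q₂ = 0.7811, √V(0.5) = 0.1058, √V(0.85) = 0.0565. The argument is (0.35 − 2.576 × 0.1058)/0.0565 = 1.37, so power is 0.915. Solving for 90% gives 49+9 against the stated 48+9, and the other cells agree within about 1–2 patients. The 57 is what this method yields.

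**Step 2: let the split vary.** With 57 evaluable, negatives follow Binomial(57, 0.1497): mean 8.5, SD 2.7. The chance of fewer than 9 is 0.51, and of 6 or fewer 0.23. Power by number of negatives (total 57):

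| Negatives | 5 | 6 | 7 | 8 | 9 | 10 | 11 |
|---|---|---|---|---|---|---|---|
| Power | 0.49 | 0.66 | 0.78 | 0.86 | 0.915 | 0.947 | 0.966 |

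**Step 3: average over the binomial distribution.**

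| Case | 57 evaluable | 63 evaluable |
|---|---|---|
| Negatives the minority, ratio 0.176 | 0.812 | 0.871 |
| Negatives the minority, 48/57 positive | 0.840 | 0.894 |
| Positives the minority, ratio inverted | 0.751 | 0.806 |

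With 63 enrolled and each patient lost independently with probability 10%, the first row gives 0.807. About 67 evaluable per type would bring its average to 0.90.

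The third row differs because the formula is not symmetric in the two classes. With 9 positives and 48 negatives held fixed, it already gives only 0.82.

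**Step 4: check by simulation.** With binormal scores at AUC 0.85 and a two-sided rank-sum test at 0.01, power is about 86.5% with 48+9 fixed and about 79% with the random split at 57. The drop is similar, from a lower starting point.

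**Step 5: pool the four types.** With 4 × 57 = 228 evaluable patients, average power exceeds 0.999.

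**The case against.** **The table is correct, and planning on the expected ratio is ordinary practice.** Both are true. A reader might infer an arithmetic error in the 57; there is none, since the figure reproduces. What does not carry over is the 90%, which belongs to a fixed split.

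**The extra 10% covers the gap.** The protocol assigns that margin to loss to follow-up and incomplete data. Even with no loss, power is about 87% (89% using 48/57).

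**No analysis by surgery type is described.** This has weight. The Data Collection and Statistical Analysis section names no such analysis and mentions the AUC only where appropriate, for ultrasound parameters. A reader might infer that the study as a whole is underpowered; the pooled figure rules that out on these inputs. But the sample size is justified type by type, so the per-type claim must hold as stated.

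**Positive is undefined, so the split might be fixable and the ratio might be wrong.** This stands in part. That class status is unknown at enrolment is inferred from the observational enrolment and the 30-day outcome. If positive means a complication, a ratio of 0.176 makes 85% of patients positive, while the Background reports an incidence of 8% to 40%. With positives at 8%, 20% and 40%, the same averaging at 57 gives 0.43, 0.88 and 0.99. The doubt about the ratio can therefore matter more than the random split. It is also tempting to say that the shortfall is the same whichever class is positive; the third row of the table shows that it is not.

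**Conclusion.** The point holds for the per-type power. On the protocol's own inputs the design gives about 81% with 57 evaluable patients (84% with 48/57) and about 87% with all 63 (89% with 48/57), not 90%. If positives are the minority, it is about 75% at 57. These figures rest on a null AUC of 0.5, two-sided testing, the ratio of 0.176 and class membership not known at enrolment.

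Two stronger readings are not supported. The 81% is not a single answer, because it supposes that the full 10% is lost. Nor can one say that 90% is secured once 9 negatives are seen: that holds under the approximate formula, but the rank-sum test gives about 86.5% at 48+9. Part of the distance from 90% to the simulated 79% is therefore the formula's approximation rather than the random split.

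The design is not invalidated. A stated property is too favourable, and the correction is cheap.

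**What to change.** Keep 63 per surgery type. In the Sample Size Estimation section:

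- State which patients are positive, and confirm that the ratio of 0.176 is the right way round for that definition. If it is not, recompute the figures below.
- Replace the 90% power per type with wording such as: *about 81% with 57 evaluable patients and 87% with 63 evaluable, averaged over a class split not fixed by design, for AUC 0.85 against 0.5 at two-sided alpha 0.01, assuming a negative-to-positive ratio of 0.176; power is lower when fewer than 9 patients fall in the smaller class.*
- Report the observed class counts with each AUC.

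The cost is a few reworded sentences and a less favourable stated power. No patients or procedures are added.

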## Objective

To evaluate the clinical association between intraoperative paravertebral block (PVB) and the reduction of postoperative complications in patients undergoing thoracic surgery.

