### **Descriptive statistics:**

Continuous variables: presented as mean  $\pm$  standard deviation (SD) and confidence intervals (CI); when necessary, minimum, maximum, 25th percentile, median, and 75th percentile will be reported.

Paired continuous variables: differences reported as mean  $\pm$  SD.

Non-parametric data: reported as median and mean ranks.

Categorical variables: presented as frequency distributions and percentages.

Ordinal variables: presented as frequency distributions, percentages, median, and mean ranks.

Binary/qualitative variables: reported as positivity rate, number of positive cases, and total sample size.

**Diagnostic evaluation:** When appropriate, the area under the receiver operating characteristic curve (AUC) will be calculated to assess the predictive value of ultrasound parameters.

**Effect analysis:** Associations and predictive effects will be evaluated using correlation analysis, multivariable linear regression, logistic regression, Cox proportional hazards models, and Kaplan-Meier survival analysis.

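### The 90% power and the 57/63/252 figures belong to one unnamed ROC curve and do not cover the stated objective on PVB and complications; 50–100 prospective patients are also given beside 252

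*Protocol*

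**What the plan says.** The Objective section has one aim: "To evaluate the clinical association between intraoperative paravertebral block (PVB) and the reduction of postoperative complications". Under Prospective Analysis, PVB and MMP3 are both to be related to complications and the findings checked against the retrospective results.

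Sample Size Estimation contains one calculation. Its inputs are a significance level of 0.01, power of 0.90 and "Area under the ROC curve (AUC, AZ) = 0.85; Ratio of negative to positive groups = 0.176". From the table cell 48+9 it concludes that "the required total sample size for this study is 57 patients", adds 10% to reach 63 per surgery type, and multiplies by four to reach 252. It states no complication rate, PVB effect, PVB share or marker. Earlier in the same section, for the prospective component, "the anticipated sample size is approximately 50–100 patients".

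The analysis section calculates an AUC only where appropriate, to "assess the predictive value of ultrasound parameters". Ultrasound parameters are not among the variables listed in Study Design or Study Procedures.

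The retrospective part is a count of 2,000 cases with no power or precision statement. Study Design describes these patients as having had PVB. Sample Size Estimation and Retrospective Analysis describe thoracic surgery patients generally.

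**The concern.** An AUC calculation asks how well one marker separates two groups of patients. The objective asks whether complication rates differ by PVB use. The first gives no information about power for the second, yet the result is presented as the size the whole study requires.

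If the 90% is read as power for the objective, a prospective result showing no clear PVB difference would count for more than it should. This matters because the prospective findings are to be validated against the retrospective ones: failure to agree could reflect size alone. Two prospective sizes in one section also leave it unclear when enrolment is complete.

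**Working it through.** **1. Reproducing 57, 63 and 252.** Inputs from Sample Size Estimation: AUC 0.85, negative:positive ratio k = 0.176, alpha 0.01, power 0.90. The null AUC is not stated; 0.5 is assumed. Sidedness is not stated; two-sided fits the table.

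Hanley–McNeil, large-sample form, with Q1 = A/(2−A), Q2 = 2A²/(1+A) and W(A) = (Q1−A²)/k + (Q2−A²):

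- W(0.5) = 0.0833/0.176 + 0.0833 = 0.557
- W(0.85) = (0.739−0.7225)/0.176 + (0.781−0.7225) = 0.153
- Positives = [(2.576·√0.557 + 1.282·√0.153)/0.35]² = 47.9, so 48
- Negatives = 0.176 × 47.9 = 8.4, so 9

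The total is 57, as stated. Then 57 × 1.1 = 62.7, so 63, and 63 × 4 = 252. With the finite-sample variance, 48+9 has power Φ((0.35 − 2.576×0.1058)/0.0565) = Φ(1.37) = 0.915. The 90% is therefore power for one AUC within one surgery type.

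**2. Dependence on the mix.** In 48+9, 84% of patients are positive (48/57). The protocol does not define positive. If it means a complication, the Background range of 8–40% gives about 5 to 23 positives among 57 (57 × 0.08 = 4.6; 57 × 0.40 = 22.8). By the same finite-sample formula:

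| Positive + negative | Power, AUC 0.85 v 0.5, two-sided alpha 0.01 |
|---|---|
| 48+9 | 92% |
| 5+52 | 50% |
| 9+48 | 82% |
| 23+34 | over 99% |

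**3. The PVB comparison at 252 patients.** Assumptions, none of them in the protocol: a 1:1 split (126 v 126), a 30% or 50% relative reduction, and alpha 0.01 or 0.05. The protocol's 0.01 is listed for the AUC calculation, and no alpha is given for the PVB test. The rate without PVB is taken from the Background range.

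Power = Φ((d − z·s0)/s1) + Φ((−d − z·s0)/s1), where d is the difference in rates, s0 its standard error with pooled variance and s1 its standard error without pooling.

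- 40% v 28%: d = 0.12, s0 = 0.0597, s1 = 0.0592, so Φ(−0.570) = 28.4%; the second term is negligible.
- 8% v 5.6%: d = 0.024, s0 = s1 = 0.0317, so Φ(−1.82) plus a very small second term = 3.5%.

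| Rate without PVB | 30% red., α 0.01 | 30% red., α 0.05 | 50% red., α 0.01 | 50% red., α 0.05 |
|---|---|---|---|---|
| 8% | 3.5% | 12% | 11% | 27% |
| 15% | 6.6% | 19% | 24% | 47% |
| 24% | 12% | 29% | 46% | 70% |
| 40% | 28% | 52% | 82% | 94% |

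An uneven split can move power either way. With 70% receiving PVB (30% reduction, alpha 0.01) it rises from 3.5% to 4.2% at a rate of 8% and falls from 28% to 25% at 40%.

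**4. The 2,000 retrospective cases, only if they include a no-PVB group.** Same formula, 30% reduction, alpha 0.01, rates of 8/15/24/40%: 33/67/92/over 99% at 1:1, and 15/29/49/82% if 90% received PVB.

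**The case against.** The AUC calculation is not detached from the study. Study Design includes a clinical-correlation aim on biomarkers predicting prognosis and recovery, and Prospective Analysis adds MMP3. A ROC calculation is a plausible basis for that aim, and its AUC input is printed openly. This stands: a reader might infer that the calculation serves no purpose in the study, and the documents do not support that. What remains is that no marker is named, the analysis section ties the AUC to something not collected, and the result is labelled as the size for the whole study.

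The power figures for PVB rest on assumed effects, split and alpha. This also stands. A reader might infer that the prospective part has only a few per cent power, but that holds only at the low end. One scenario, a 50% reduction from 40% at alpha 0.05, reaches 94%. The mismatch itself needs none of these assumptions.

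The 50–100 figure may be a prior expectation from similar studies, or a per-type figure, since 57 and 63 both lie within it. A reader might infer a rival target and a plan to stop at 100; the text does not say so. It does leave two prospective sizes unexplained.

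Finally, one might say that the 2,000 cases carry the objective. They can do so only with a comparator, and Study Design, read literally, provides none.

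**Conclusion.** The concern holds in this form: 57, 63 and 252 are correctly computed for one AUC, but are wrongly presented as the required size for the study. They bear at most on the biomarker-prediction aim, and there the 90% holds only for the 48:9 mix against a null of 0.5 at two-sided alpha 0.01. For the sole stated objective the protocol gives no power. Under a 1:1 split and a rate of 8–40% without PVB, the illustrative range at 252 patients is about 3.5–28% (30% reduction) or 11–82% (50% reduction) at alpha 0.01, and 12–52% or 27–94% at 0.05. The 50–100 and 252 figures need reconciling.

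A reader might go further and infer that the negative:positive ratio was entered the wrong way round, because 84% positive sits oddly with complication rates of 8–40%. The protocol does not say what positive means, so that cannot be concluded; the definition has to be supplied.

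**What to change.** Change the wording of the protocol; no patients need be added.

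1. State that 57 evaluable patients per surgery type give about 90% power for AUC 0.85 against 0.5 with 48 positive and 9 negative patients. Name the marker and define positive. If positive means a complication, recompute with the expected mix.
2. Keep one prospective target, 252 (63 per type), and delete or explain the 50–100 figure.
3. State that the prospective PVB–complication contrast is not powered by this calculation and will be reported as an estimate with a confidence interval.
4. Reconcile Study Design, where the retrospective patients had PVB, with Sample Size Estimation and Retrospective Analysis, which describe thoracic surgery patients generally. Only if a no-PVB group exists, state the detectable difference for the 2,000 cases at the actual PVB split.

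The cost is redrafting, plus a count of PVB use in the 2,000 cases for item 4. If that count finds no patients without PVB, the retrospective part cannot make the comparison and the protocol would have to say so. The downside is that the stated power for the main objective becomes less favourable.
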